HOPE Social Media Intervention for HIV Testing and Studying Social Networks

NCT02944877

May 1, 2014

Research Design and Methods

Participants. Participants from Greater Los Angeles will be recruited in 5 waves (approximately 120 participants and 18 peer leaders per wave). Participant inclusion criteria are as follows: 1) 18 years of age or older, 2) biologically male and self-identified as male, 3) has had sex with a man in the past 6 months, 4) has a Facebook account, 5) currently living in Greater Los Angeles, 6) self-reported HIV negative or unknown serostatus, and 7) African American and/or Latino.

Participant Recruitment. Participants in both the control and intervention group will be recruited through 3 methods: (a) through the help of community organizations such as the Los Angeles Gay and Lesbian Center who will provide referrals and fliers to participants; (b) through advertisements and fliers at local gay organizations, clubs/bars and universities; and (c) through Internet recruitment methods such as postings on discussion forums on Craigslist.org, banner Internet and social media advertisements targeted toward at-risk populations, and a Facebook “fan page.” Banner ads will be tailored to ethnic background as this has been found to increase online recruitment (55). An independent website (including access for mobile/phone viewing) will also be created listing a study description, criteria for participation, and contact information.

Participants will be recruited and informed about the potential benefits of participating in the study: (a) meet other men with similar backgrounds and interests, (b) learn how to overcome shyness by meeting other people and learning about their methods of communicating with others, (c) learn how to live a healthy lifestyle, and (d) meet and befriend cool and popular people within the same community (see human subjects section), including the right to refuse participation and a confidentiality statement.

The Facebook Connect “application” is a computer science method that helps reduce likelihood of people registering multiple times (multiple respondents). The application requests participants to enter their Facebook username and password and uses Facebook “API’s” to connect to Facebook and authenticate that the participant is a valid Facebook user. While this process may reduce recruitment numbers compared to studies not using this approach, it can improve data quality by verifying that participants are unique Facebook users. This process will also help to screen out participants who might try to falsely report HIV status to enroll in the study. Authentication such as through Facebook Connect has become a standard procedure when downloading mobile “applications” and registering for Websites (45,56). Further, this process will be used to analyze data on the exploratory aim (an alternative method of collecting social network data). Participants will have been informed during consent that we will collect information on their social networks characteristics (among those who provide access), including changing number of friends, and that we can collect these social network data through either weekly screenshots of their profiles, or through them accepting us to access these data from the Facebook application. If participants allow this Facebook application to store their social network data, we will store these data. Otherwise, we will use this application to verify with Facebook that the participant is a unique Facebook user, but no information will be stored.

Study Design and procedures. This is a 2-group cluster randomized controlled study with repeated measures at post (12-week) intervention and 6-month and 1-year follow-up. Participants will be randomly assigned to an experimental or control condition. Peer leaders will be randomly assigned to communicate with participants in their cluster. Peer leaders in the control group will follow the same methods as the experimental group but will focus on general health rather than HIV prevention. Peer leaders will be able to contact participants through Facebook email, chatting (which is done from within the Facebook platform by seeing that other members of the group are online), and by posting comments, pictures, and videos on the group webpage.

At the beginning of the study, participants will be asked to log onto their Facebook accounts (to ensure privacy settings allow for accepting Facebook group emails), and to be receptive to communicating with others in the group. However, once participants have joined the group they will be told to use Facebook as they would normally, with no obligation to interact with peer leaders or remain a part of the group. Participants will be asked to complete a baseline and 3 follow-up questionnaires: 1) at completion of their 12-week interactions with peer leaders (post-intervention), 2) at 6 months after the post-intervention questionnaire (6-month follow-up), and 3) at 12-months after the post-intervention questionnaire (12-month follow-up). During the 12-week intervention, participants will be emailed to inform them that they can receive a free home-based HIV test for participating in the study.

C3: Measures. All questionnaire items will be in both English and Spanish.

Demographics.

Sexual history and risk behaviors. Participants will be asked to report recent and overall number of sexual partners and sexual risk behaviors (e.g., types of sexual intercourse, condom use and health service usage). Items are adapted from the Center for AIDS Prevention Studies (CAPS) HIV measurement tools (58), and tailored for AA and Latinos. For reliability and validity see Koblin, Chesney, Husnik, et al. 2003 (59). Although our preliminary studies found reduced sexual risk behaviors among both intervention and control groups participants (with greater reduction among intervention group members), it is possible that a social networking-based intervention might increase sexual risk behaviors. We have therefore included sexual risk measures to assess how the intervention might impact sexual risk behaviors.

Testing Rates and linkage to care. Participants can request an HIV home test to be mailed to them by emailing the study coordinator and providing an address to receive the test. Tests will be mailed along with an instruction kit and pre-paid addressed labels to return the test to the laboratory. Each kit will have a unique identification number that can be used to track participant results. Participants will be able to access results by calling the number on the testing kit. The kit manufacturer/laboratory will provide us with data (de-identified numbers linked to participants) on participants who returned the testing kit, followed-up for results, and the test result.

Test Result. HIV testing will be performed using the Home Access Express HIV-1 Test System. This FDA-approved kit requires a finger stick sample for analysis. Test results are anonymous and provided only by a specific code number. Users complete the home test themselves at their preferred time, and mail the sample to Home Access directly. The Home Access lab completes the tests within 24 hours and participants can call an 800 number to obtain results. If HIV positive, they are provided with free counseling by counselors trained in pre and post-test counseling. As with any Internet study and many non-Internet studies, there is a possibility that the person testing is not the study participant. However, this is unlikely as participants are not required to test and therefore might be more inclined to be honest as they are testing out of interest. Although oral, fluid, rapid, HIV self-tests have been FDA-cleared and are available for use (by Orasure) , Home Access “mail-in” tests are being used for this study to verify whether the test has actually been used and to have access to test results. Although it would be possible to request participants to mail us their results from an oral test, in our interviews of testing methods, participants have indicated that they be reluctant to mail us a test showing they were positive if they had just tested HIV positive. We therefore think that using the Home Access mail-in home-based tests would improve data quality for this study.

C4: Data Analysis

C4.2 STATISTICAL ANALYSIS

Planned Analyses. Chi square tests at $p < .05$ significance level will measure baseline demographic differences between intervention and control groups. All analyses will include random effects to allow for correlation among subjects within clusters. Comparisons of proportions (including demographic differences) will use mixed effect logistic models. Fixed effects will be used for group differences, and for covariate adjustments; random effects will be used to model cluster correlations. We will use the Poisson distribution to model count data, again checking for larger than expected variation, which for sexual experience data is not uncommon. For evaluating changes from baseline in self-report data, longitudinal modeling (68,69) will be used, as this is likely to increase power. Stata modules *xtlogit* and *xtmepoisson* will be used to fit and evaluate the clustering for binary and Poisson outcomes, respectively. An alternative to mixed effects modeling, generalized estimating equations, implemented through the Stata command *xtgee* will be done and compared to the mixed effects modeling. No formal adjustments for multiple comparisons are planned; however for the differences anticipated, the power is adequate to accommodate simple Bonferroni adjustments for post-intervention and 12-month follow-up.

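### The arm test has no small-sample method in any case, and wave is not named in any model; wave belongs in the testing-outcome model only if arms are balanced within wave and clusters number about 20 or more

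*Combined protocol and SAP*

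**What the plan says.** Under Participants, men "will be recruited in 5 waves (approximately 120 participants and 18 peer leaders per wave"). Under Study Design and procedures the trial is a two-group cluster randomised study. Allocation is described in two sentences: "Participants will be randomly assigned to an experimental or control condition" and "Peer leaders will be randomly assigned to communicate with participants in their cluster". The document gives no cluster count or cluster size, no allocation ratio, and no statement that randomisation is stratified by wave.

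Under Testing Rates and linkage to care, kit return is recorded by the laboratory: "The kit manufacturer/laboratory will provide us with data (de-identified numbers linked to participants) on participants who returned the testing kit". It is an outcome with no baseline value.

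In C4.2, Planned Analyses, the model terms are: "Fixed effects will be used for group differences, and for covariate adjustments; random effects will be used to model cluster correlations". The covariates are not listed. The Stata modules xtlogit and xtmepoisson "will be used to fit and evaluate the clustering for binary and Poisson outcomes, respectively", with generalised estimating equations as a comparison. No small-sample correction is named for either approach. For change in self-reports the plan says: "For evaluating changes from baseline in self-report data, longitudinal modeling (68,69) will be used, as this is likely to increase power".

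On baseline comparisons, C4.2 says that chi-square tests at the 5% "significance level will measure baseline demographic differences between intervention and control groups". The same paragraph then requires random effects in every analysis and assigns comparisons of proportions, demographics included, to mixed logistic models.

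**The concern.** There are two linked gaps and one minor inconsistency.

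First, in a cluster trial the information on the arm effect is limited by the number of clusters. A normal reference for a random-effects model is adequate when clusters are many and too liberal when they are few. The plan does not say which situation applies, and names no method that is safe in both.

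Second, participants enter in five successive waves. If waves differ in willingness to test and the model has no wave term, that variation is absorbed into the cluster variance. With arms balanced within wave, the arm estimate stays unbiased but its standard error is larger than it need be. This bears mainly on single post-baseline outcomes such as kit return. In self-reported change from baseline, a wave difference that is constant over time largely cancels. The plan itself prefers longitudinal models for their power, so precision is one of its own aims.

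The two gaps interact: a wave term uses four more degrees of freedom and makes an uncorrected z test more liberal.

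**Working it through.** **Inputs.** From the document: 5 waves of about 120 participants and 18 peer leaders, so 5 × 120 = 600 participants and 5 × 18 = 90 leaders. There is no stated power, effect size or intracluster correlation to reproduce. Assumed: 600 participants in equal arms; k = 10 to 90 clusters of m = 600/k; 30% kit return; wave share tw and cluster share tc of the outcome variance from 0 to 0.05 (logit SD = √(share/0.21), where 0.21 = 0.3 × 0.7); a two-sided 5% Wald z test for the planned model, since the plan names no other.

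**1. Planned model without wave.** If the arm statistic follows t on k − 2 degrees of freedom, using 1.96 gives a true level of 8.6% (k = 10), 6.6% (20) and 6.0% (30). Simulated null rejection for a random-intercept logit with Wald z (600 runs, Monte Carlo error 1 to 2 points, arms balanced within wave), for (tw, tc) = (0, 0.01), (0.01, 0.01), (0.05, 0.05):

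| k | without wave, % | with wave, % |
|---|---|---|
| 10 | 8.2, 7.2, 9.0 | 11.8, 13.5, 22.0 |
| 20 | 5.3, 5.5, 3.3 | 6.3, 9.2, 12.0 |
| 30 | 5.2, 4.3, 4.0 | 5.5, 5.7, 9.5 |
| 40 | 6.5, 6.0, 4.0 | 6.5, 7.7, 8.3 |
| 90 | 4.8, 5.8, 3.8 | 5.5, 6.3, 4.8 |

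A second set of runs (20% return, 2000 per setting, cluster share 0.02 or 0.05) gave 8.4 to 10.5% at k = 10 without wave when waves did not differ. With wave differences (logit SD 0.3 or 0.5) it gave 3.9 to 8.4% when arms were balanced within wave, and 9.0 to 9.9% when allocation ignored wave (cluster share 0.02 only). In the first set, a cluster-level t test with wave held 4.6 to 5.3%; in the second, 4.7 to 5.8%.

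**2. Cost of the t reference.** Interval width relative to 1.960, without wave: 2.306/1.960 = 1.177 (k = 10), 2.101/1.960 = 1.072 (20), 2.048/1.960 = 1.045 (30).

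**3. Precision lost without wave, arms balanced within wave.** SE without wave / SE with wave = √[(tw + tc + (1 − tw − tc)/m) / (tc + (1 − tw − tc)/m)].

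- k = 20, m = 30, shares 0.01: √[(0.02 + 0.98/30)/(0.01 + 0.98/30)] = √(0.0527/0.0427) = 1.11. After the t penalty: 1.11 × 2.101/2.145 = 1.09.
- k = 20, shares 0.05: √(0.13/0.08) = 1.27; after the penalty, 1.25.
- k = 10, m = 60, shares 0.01: 1.17; after the penalty, 1.17 × 2.306/2.776 = 0.98 (1.174 unrounded), so the gain is gone.
- tw = 0: the ratio is 1.00 for every k.

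**4. Power, 30% v 40%, cluster-level t test, without → with wave.** Columns are (tw, tc).

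| Setting | (0, 0.01) | (0.01, 0.01) | (0.05, 0.05) |
|---|---|---|---|
| Balanced, k = 10 | 43 → 35 | 32 → 35 | 10 → 16 |
| Balanced, k = 20 | 57 → 55 | 49 → 56 | 19 → 29 |
| Balanced, k = 30 | 61 → 61 | 57 → 62 | 27 → 38 |
| Balanced, k = 90 | 68 → 68 | 68 → 69 | 49 → 57 |
| Both arms in each wave, not balanced, k = 20 | 56.7 → 50.0 | 49.0 → 48.8 | 21.8 → 27.9 |
| Both arms in each wave, not balanced, k = 30 | 60.5 → 54.3 | 55.3 → 55.0 | 30.0 → 34.6 |

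Repeat runs for balanced arms, k = 20, gave 47 to 48% → 54% at shares 0.01 and 19 to 20% → 31% at 0.05. Without balance, the gain at shares 0.01 disappears and the cost when waves do not differ is 6 to 7 points.

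**5. Baseline chi-square.** With design effect D = 1 + (m − 1) × ICC, the true level is 2[1 − Φ(1.96/√D)]. At an assumed baseline ICC of 0.02, D = 2.18, 1.58 and 1.38 for k = 10, 20 and 30, giving about 18%, 12% and 10%. At ICC 0 it is 5%.

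**The case against.** Much of the opposing case stands.

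- The covariate list is open, so wave is unnamed rather than excluded. This stands, although a covariate left unnamed is not pre-specified.
- Nothing in the document shows that waves differ: there is one region, one set of criteria and one set of recruitment methods. The larger gains rest on a wave share of 0.05, where waves one standard deviation either side of the mean would return about 21% and 41% of kits. This stands, and the size is therefore conditional.
- A reader might infer that having both arms in every wave is reason enough to add wave. The not-balanced rows above show otherwise, and the document does not state stratification by wave.
- A reader might infer that the planned test is conservative because wave is left out. That describes a cluster-level t test with balanced arms. The planned model with Wald z is generally liberal at about 10 clusters, and the need for a small-sample method exists apart from wave.
- The power figures use the cluster-level t test, not the planned model, and only one binary outcome was simulated. They do not measure the loss under the plan as written, and say nothing about count or longitudinal outcomes.
- The published text goes from C4 to C4.2 and mentions anticipated differences and adequate power without figures. The cluster count may stand in a section that is not public.
- If individuals are randomised and then placed in clusters, the baseline ICC should be near zero and the chi-square would do little harm. The contradiction in wording remains.

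**Conclusion.** The point holds in a limited form and merits a change to the analysis plan. The firmer part is the missing small-sample method. At about 10 clusters the Wald z test has a true level of about 7 to 10% in most settings examined, lower only where sizeable wave differences are balanced across arms. At 20 or more clusters without wave the excess is small and fades.

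The wave part is conditional. If arms are balanced within wave and waves differ, omitting wave loses precision on kit return and similar outcomes: about 7 power points at 20 clusters with shares of 0.01, and 10 to 12 with shares of 0.05, under the assumed rates. If waves do not differ there is nothing to gain. The documents do not support a reading that omission biases the arm effect under balanced allocation, or that wave should be added whatever the design. Adding it with a z test would raise the false-positive rate to 12 to 22% at 10 clusters and 6 to 12% at 20.

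The chi-square inconsistency is real but confined to the baseline table, and would not merit a point by itself.

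**What to change.** 1. State the number of clusters, the unit of randomisation and whether allocation is balanced (stratified) within wave, and list the covariates.
2. Test the arm effect with a small-sample method in all cases, for example a cluster-level t test on clusters minus 2 degrees of freedom without wave, or clusters minus 6 with it.
3. Add wave as a five-level fixed effect to the testing-outcome model only if arms are balanced within wave and there are about 20 or more clusters. Otherwise use it as a sensitivity analysis only.
4. Reconcile the baseline chi-square sentence with the random-effects rule, either by dropping the tests and describing baseline by arm or by following the mixed-model sentence.

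Cost: plan wording and one extra test procedure. The t reference widens intervals by about 18% at 10 clusters, 7% at 20 and 4 to 5% at 30. With 20 or more balanced clusters, wave costs about 1 to 2 power points if waves do not differ. Without balance it can cost 6 to 7 points, which is why it should not then be primary.

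### Self-report outcomes are evaluated as change from baseline with no stated baseline adjustment or common baseline mean; naming one would gain power if a free-baseline contrast is what will be fitted

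*Combined protocol and SAP*

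**What the plan says.** C4.2 (Planned Analyses) covers self-report outcomes in one sentence: "For evaluating changes from baseline in self-report data, longitudinal modeling (68,69) will be used, as this is likely to increase power". The general model structure is: "Fixed effects will be used for group differences, and for covariate adjustments; random effects will be used to model cluster correlations". For counts: "We will use the Poisson distribution to model count data, again checking for larger than expected variation". The models are mixed logistic and mixed Poisson, with generalized estimating equations (GEE) as a comparison. No covariate is named. The section does not say that the baseline value of the outcome enters the model or that the arms share a baseline mean. It does not say the opposite either. The two references cited for the method are not available here.

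The outcomes concerned are in C3 (Measures, Sexual history and risk behaviors): "Participants will be asked to report recent and overall number of sexual partners and sexual risk behaviors". Their purpose is stated there, after a remark that the intervention could raise risk behaviour: "We have therefore included sexual risk measures to assess how the intervention might impact sexual risk behaviors".

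Study Design and procedures supplies the rest. On data: "Participants will be asked to complete a baseline and 3 follow-up questionnaires". On design: "This is a 2-group cluster randomized controlled study with repeated measures". On allocation: "Participants will be randomly assigned to an experimental or control condition".

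**The concern.** The usual way to turn change from baseline into a two-arm repeated-measures model is an arm-by-time interaction, with each arm's baseline mean estimated freely. Under random assignment the two baseline means are equal in expectation. Estimating their difference and subtracting it adds noise without removing bias. A model that adjusts for baseline, or holds the arms to one baseline mean, uses the same data more efficiently.

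The cost would fall on the sexual-risk items. They are in the study partly to detect a possible harm, and a null result on such a check reassures less when power is lower. The plan calls its power adequate but prints no figure, so there is no documented margin to absorb a loss.

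**Working it through.** **No figure to reproduce.** The documents give no power, effect size, correlation, ICC or cluster size for self-report outcomes.

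**Inputs**
- From the documents: random assignment, clustering, one baseline and three follow-up questionnaires, and 5 waves of about 120 participants (5 × 120 = 600).
- Assumed: correlation r between a person's baseline and follow-up values of 0.3, 0.5 or 0.7; equal variances; a cluster effect that arises after baseline, since peer leaders start communicating with their clusters after assignment; a design effect of 1 + c, with c = (m − 1) × ICC for cluster size m; two-sided 5% tests.
- 80% power is a reference point, not a figure from the plan.

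**Linear-scale variances for one follow-up (common factor dropped)**
- Free-baseline change contrast: 2(1 − r) + c
- Baseline-adjusted or common-baseline: 1 − r² + c
- Follow-up only, ignoring baseline: 1 + c

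The first exceeds the second by (1 − r)², which is positive for every r below 1. With R = [2(1 − r) + c] / [1 − r² + c], an analysis that has 80% power with adjustment has power Φ(2.8016/√R − 1.96) as a change contrast.

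At design effect 2 (c = 1):
- r = 0.3: R = 2.4/1.91 = 1.26; power 70.5%
- r = 0.5: R = 2.0/1.75 = 1.14; power 74.6%
- r = 0.7: R = 1.6/1.51 = 1.06; power 77.7%

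Range over design effects, R (power):

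| Design effect | r = 0.3 | r = 0.5 | r = 0.7 |
|---|---|---|---|
| 1.5 | 1.35 (67.5%) | 1.20 (72.5%) | 1.09 (76.6%) |
| 2 | 1.26 (70.5%) | 1.14 (74.6%) | 1.06 (77.7%) |
| 3 | 1.17 (73.6%) | 1.09 (76.5%) | 1.04 (78.6%) |

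Without clustering R is 1.54, 1.33 and 1.18; these are upper bounds.

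**Against ignoring baseline.** The ratio [2(1 − r) + c]/(1 + c) at c = 1 is 2.4/2 = 1.20, 2.0/2 = 1.00 and 1.6/2 = 0.80. At a single follow-up, the free-baseline contrast therefore beats follow-up only when r exceeds 0.5.

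**Logit and log scales, by simulation.** Each arm had 300 participants (1:1 assumed), as 15 clusters of 20 or 5 of 60, with a design effect of about 2. The change contrast came from a saturated marginal model. Adjustment was a follow-up regression on arm and baseline. Relative efficiency is the squared ratio of mean/SD of the estimates, which allows for the coefficient changing meaning under adjustment. Results at r of about 0.3, 0.5 and 0.7:
- Binary, 50% prevalence: 1.22–1.28, 1.12–1.14, 1.05–1.07
- Counts, mean 3, overdispersed, baseline as log(1+count): 1.25–1.28, 1.11–1.12, 1.04–1.05
- The same counts with the raw baseline count: 1.25–1.26, 1.04–1.05, 0.77–0.87

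The raw count can thus do worse than the change contrast at high r. A separate count simulation gave about 1.35, 1.15 and 1.10 at r of about 0.25, 0.46 and 0.67, both for log(1+baseline) adjustment and for a common baseline mean.

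**Mixed-model check.** Random-intercept logistic fits (300 replicates, Monte Carlo error roughly 0.1) gave 1.19 and 1.34 at r of about 0.3, and 1.12 and 1.07 at about 0.5. The values near 0.5 cannot be told apart from 1 at that precision. No mixed Poisson check was run.

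**The case against.** **The plan may already do this.** Nothing in C4.2 commits to a free baseline. Covariate adjustment is foreseen in general terms, and the cited references may specify a common-baseline model. This stands: the loss is conditional, and no actual loss has been shown.

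**The power rationale is not wrong on its face.** A reader might infer that the plan prefers change to baseline adjustment because it expects more power, and that this belief is mistaken. The sentence does not support that. It gives power as the reason for longitudinal modelling, and a longitudinal model with a common baseline mean would satisfy it.

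**Failure below r = 0.5 depends on the comparator.** A reader might also infer that the rationale fails whenever r is under 0.5. That holds only against one follow-up with baseline ignored. With equal correlation among all four measurements, the change contrast averaged over three follow-ups has variance (1 + 2r)/3 + 1 − 2r = 4(1 − r)/3. This equals the single-follow-up variance of 1 at r = 0.25. The plan's remark on Bonferroni adjustment at two time points suggests contrasts by visit, so 0.5 is not irrelevant, but it is not a general threshold.

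**Within-arm change may be of interest.** C3 reports preliminary reductions in both arms, and both arms use Facebook groups. A regression of follow-up on baseline and arm gives only the between-arm contrast, and separate fits by visit would give up the joint repeated-measures model. Both points stand and shape the fix.

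**Evidence on the exact planned models is thin.** This also stands. The ordering follows from the linear algebra and from marginal-model simulation; the mixed-model check is imprecise.

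**Conclusion.** The point holds as an efficiency improvement. The plan evaluates change from baseline without stating baseline adjustment or a common baseline mean. If each arm has a free baseline, the contrast is valid but its variance at design effect 2 is about 1.26, 1.14 or 1.06 times that of the better analysis at r = 0.3, 0.5 or 0.7. That takes 80% power to about 70%, 75% or 78%. Over design effects of 1.5 to 3 the loss runs from about 12 points (r = 0.3) to between 1 and 2 points (r = 0.7).

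These sizes rest on assumed r, ICC, cluster size and, in the simulations, 1:1 allocation. The loss is zero if an adjusted or common-baseline model was already intended. A reader might infer an error, a bias or a threat to the HIV testing comparison. The documents support none of these: the contrast is unbiased under random assignment, and testing is measured by kit return, not by the questionnaires. The change is worth making because it is nearly free and because some of the affected items serve as a check for harm.

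**What to change.** Keep the mixed logistic and Poisson models, the GEE comparison and all three follow-ups. State that the between-arm effect at each follow-up is estimated with the arm means constrained equal at baseline: time terms and arm-by-follow-up terms, but no arm term at baseline. Within-arm changes from baseline can still be reported from this model.

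Alternatively, model the three follow-ups jointly with the baseline value of the same outcome as a fixed-effect covariate. For counts, enter it as log(1+count) and not as the raw count.

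The cost is wording and slightly more model specification. Baseline questionnaires are already collected, and fixed-effect covariates and cluster random effects are already planned. One downside must be stated: with baseline as a covariate in the logistic model, the odds ratio is conditional on baseline and is larger in size than the unadjusted one. A common-baseline GEE avoids that change of estimand.
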